3.1 Study Design

The enrollment of participants initiates relevant processes immediately. After the completion of preoperative examinations, participants with corneal perforation will be arranged for transplantation as soon as possible. During the usual procedure of the surgery, CRISPR/Cas9 mRNA formulation in the form of HELP will be administrated for the treatment of refractory HSK. The hospital observations of participants will persist for 7 days. The postoperative recovery condition, HSV-1 testing outcome, adverse effects of the participants will be examined at every follow-up time. After their hospital discharge on 7th day, follow-up will be conducted on 1 month, 2 months, 3 months, 6 months and 12 months after the surgery. The basic information is shown in the Table 1. below.

Table 1. Basic Information of Our Clinical Study

Item	Content
Study Type	Interventional (Clinical Trial)
Estimated Enrollment	3-6 participants
Allocation	N/A
Intervention Model	Single Group Assignment
Intervention Model Description	Single group target value: Since there is no similar products approved on the market or similar comparative treatment methods, the single group target value method is adopted
Masking	None (Open Label)
Primary Purpose	Treatment
Actual Study Start Date	November 4, 2020
Estimated Primary Completion Date	November 2021
Estimated Study Completion Date	May 2022

In this study, each participant diagnosed with terminal refractory HSK will undergo HELP injection during the normal procedure of penetrating keratoplasty (PK). Before the surgery, they will receive conventional topical or systemic antiviral treatment. During the operation, single dose CRISPR/Cas9 mRNA formulation in the form of HELP will be injected into the recipient graft bed. Then the participants will no longer receive any forms of antiviral treatment unless occurs an uncontrollable virus recurrence, when the conventional antiviral therapy continues. At follow-up visits, participants will undergo a series of examinations, including best-corrected visual acuity, intraocular pressure, photograph of anterior segment, postoperative B-scan ultrasonography, time-domain optical coherence tomography (OCT), spectral-domain OCT, electroretinography (ERG), ELISA of blood samples, deep sequencing of corneal epithelial cells, HSV-1 testing and potential adverse events.

3.2 Preparation of HELP Formulation

HELP (BD111) was produced following Good Manufacturing Practice (GMP) guidelines. Briefly, 293T cells were seeded in 10-tray stacks cell factory (Thermo Fisher Scientific) and transfected with 6 packaging plasmids using PEI. Cell culture medium was refreshed 6 h post-transfection. Supernatants were harvested 48 h later and pooled before filtration through 0.45 µm. The downstream purification process included a benzonase treatment overnight at 4°C, followed by ultrafiltration and purification using ion-exchange chromatography. The resulting BD111 was dissolved in PBS, passed through 0.22-µm filters, and stored at -80°C.

3.3 Corneal Transplant and HELP Administration

3.3.1 Preoperative Medications

The preoperative medications for participants having a PK are listed below:

- ⑩ Topical antiviral drugs: Acyclovir eye drops 6 times daily and oral acyclovir tablets 3 times daily till the day before surgery
- ⑩ Miotics: 1% Pilocarpine drops for phakic patients undergoing PK, instilled every 10 minutes for 30 minutes before the operation
- ⑩ Intravenous Mannitol 20%: Dosage of 1 g/kg given over 20–30 minutes before the operation to lower the intraocular pressure

3.3.2 Anesthesia

PK will be performed under retrobulbar block for patients with good cooperation or those who are at risk for undergoing general endotracheal anesthesia in our hospital. The procedure is performed under monitored anesthesia care, including the control of blood pressure, heart rate, oxygen saturation and anxiety. Patients should supine and look straight forward, with their heads maintained in a neutral position. After sterilization of the surgical area, a needle (27 Gauge, 3 cm long) is inserted at the inferolateral border of the bony orbit and directed straight back until its tip has passed the equator of the globe. The needle is then directed medially and cephalad toward the apex of the orbit. Upon a negative aspiration for blood, 3-4mls of local anesthetic solution is injected and the needle is then withdrawn. 2% Lidocaine (Xylocaine) is used as anesthetic agent. Patients are then draped in sterile fashion using a surgical film, which isolates eyelashes from the sterile field.

3.3.3 Procedural Technique

After the placement of a lid speculum, an appropriately sized trephine (usually 6.5-7.5mm) marks the epithelium on the host cornea prior to trephination. Once centered, trephination to approximately 90% depth is performed. Through the base of the trephination groove enters the anterior chamber using a 75 blade. The cornea is then carefully removed using corneal scissors, avoiding any inadvertently cutting or straying outside of the groove. After removing the cornea, viscoelastic is instilled to maintain the anterior chamber and provide protection to the intraocular tissues. The removed host tissue will be sent to pathology for pathogen detection.

The donor corneal button is cut endothelial side up using a trephine-loaded punch instrument, which should be completed prior to trephining the host. In globe perforation participants, donor grafts should be oversized by 0.5-0.75 mm compared with the host bed. Once the donor button is cut, the tissue is carefully protected for later use. Before transferring to the recipient bed, the donor graft is irrigated to remove storage solution. 10-0 nylon suture and interrupted sutures are preferred for securing the donor tissue to the host bed. Initially 4 interrupted cardinal sutures in sequence at 12, 6, 3, 9 o'clock position are performed, and 8-12 more sutures may be necessary before the graft is secure. Loose ends of the sutures should be cut short and the knots be buried in the host tissue. Finally, additional viscoelastic is applied in the angle and to the anterior chamber.

3.3.4 HELP Administration

The HELP formulation stored in -80°C will be transferred in 4 °C from the lab to the surgery room 30 min earlier. Then it will be recovered to the room temperature 10 min before its usage, where in total of 0.25 ml formulation is drawn into a 27g ophthalmic syringe for the later injection. Penetrating keratoplasty will be performed following the routine procedures described above. After sewing up the donor cornea, the HELP formulation in the syringe is injected in evenly divided 6-8 locations of the recipient graft bed. The indication for its successful entrance into the stroma will be the visible edema and whitening of the corneal bed in the injection sites, which should cover the entire recipient bed area in the end.

3.4 Post-operation Management

- ⑩ Antimicrobials: for an infectious cause, topical antimicrobials should be selected based on cultures after PK. Initially, the antibiotic should be broad spectrum with low toxicity (e.g. fluoroquinolones), typically four times daily during the first week

- ⑩ Immune Modulators: topical corticosteroid drops (such as difluprednate 0.05% ophthalmic suspension or prednisolone acetate 1.0% ophthalmic suspension four times daily (average). Steroids are tapered depending on the patient
- ⑩ Intraocular Pressure Lowering Agents: intraocular Pressure should be monitored at each postoperative visit, agents for lowering pressure should be used if significantly elevated
- ⑩ Ocular Lubricants: non-preserved artificial tears can be started early in the postoperative period to maintain and preserve the corneal epithelium

4. CRISPR/Cas9 Therapy Interruption

A CRISPR/Cas9 therapy interruption is a restart of discontinued conventional anti-viral therapy, since the CRISPR gene editing therapy is single dose applied. The CRISPR/Cas9 therapy interruption will be performed under certain conditions. As HSV-1 testing results is the main outcome of this study, the CRISPR/Cas9 therapy interruption will only be performed when virus testing outcome is at a certain range.

4.1 Criteria for CRISPR/Cas9 Therapy Interruption

- ⑩ A written informed consent was provided by the patient
- ⑩ HSV-1 testing outcome rises to excessive range (Ct value <25)
- ⑩ Noticeable corneal or systemic adverse events related to CRISPR/Cas9 therapy

5. Quality Control

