Shanghai Jiao Tong University, WF220441504

Collaborators: Key Laboratory of Systems Biomedicine,
Shanghai Jiao Tong University

Version 2.0

Version Date: April 12, 2020

Brief Summary:

The purpose of this study is to evaluate the safety, tolerability and efficacy of a single dose of CRISPR/Cas9 mRNA Instantaneous Gene Editing Therapy administered via corneal injection in participants with refractory herpetic viral keratitis.

Condition or disease	Intervention/treatment
Herpes Simplex Virus Infection	Drug: HELP (BD111) Adult single group Dose
Refractory Viral Keratitis	(Administered by corneal injection surgery. Dosage form: injection solution. Dose: 200µL. Frequency of administration: one time injection.)

Description:

This is a single-arm, single dose study of mRNA-carrying HELP (HSV-1-erasing lentiviral particles) in adult (ages 18 to 70) participants with refractory herpetic viral keratitis. 3-6 participants will be enrolled and receive HELP injection during the usual procedure of corneal transplantation. HELP is a novel gene editing formulation designed to clear Herpes simplex virus type I (HSV-1) that results in herpetic stromal keratitis in both acute and recurrent infection models which is the leading factor for infectious blindness. The main outcomes of this study include HSV-1 testing outcome, graft survival, visual acuity and adverse effects of the participants.

Outcomes Measures:

1. Primary Outcome Measure

HSV-1 testing results of the intervention eye. Tear swab of 1 week, 1 month, 2 months, 3 months, 6 months and 12 months post-operation will be collected and quantified for HSV-1 genome by real-time polymerase chain reaction (RT-PCR). The virus testing outcome was indicated as positive (+) or negative (-) by Ct values. Ct value of above 40 will be considered negative, 36-40 be considered weakly positive, and below 35 will be considered a strong positive.

2. Secondary Outcome Measure

- ⑩ Patient graft survival. The corneal grafts of participants will be monitored under a complete ophthalmic examination, including slit-lamp examination and anterior segment optical coherence tomography (OCT), at every follow up visit.
- ⑩ Best-corrected visual acuity. Changes of visual acuity of participants along the clinical trial.

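### Sections 3.1, 4 and 4.1 give unreconciled triggers for restarting antivirals, and the primary-outcome Ct bands leave 35 to just under 36 without a category

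*Combined protocol and SAP*

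**What the plan says.** All references are to the current protocol (version 2.0) unless stated.

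- **Section 3.1, Study Design.** After the injection, "participants will no longer receive any forms of antiviral treatment unless occurs an uncontrollable virus recurrence". The term is not defined, carries no Ct value and does not refer to section 4.
- **Section 4, CRISPR/Cas9 Therapy Interruption.** The word interruption has a special meaning here: "A CRISPR/Cas9 therapy interruption is a restart of discontinued conventional anti-viral therapy". The section then limits it: "the CRISPR/Cas9 therapy interruption will only be performed when virus testing outcome is at a certain range".
- **Section 4.1, criteria.** There are three bullets: written consent from the patient; "HSV-1 testing outcome rises to excessive range (Ct value <25"; and noticeable corneal or systemic adverse events related to the therapy. Nothing states how the bullets combine.
- **Outcomes Measures, Primary Outcome Measure.** Tear swabs at 1 week and at 1, 2, 3, 6 and 12 months are classified by Ct: "Ct value of above 40 will be considered negative, 36-40 be considered weakly positive", and "below 35 will be considered a strong positive".
- **Section 7 and the SAP.** The swab endpoint receives a simple descriptive summary. Neither mentions antiviral restart.

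**The concern.** The restart rule decides when a participant stops being observed on the gene-editing product without antivirals. If two sections can answer differently for the same eye, the choice falls to an investigator who is not masked, and nothing in the plan would show afterwards which section was used.

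Two things are at stake. The first is safety: section 3.4 places participants on topical corticosteroid after surgery while section 3.1 withholds antivirals, so it should be clear when antivirals come back. The second is interpretation: swabs taken after a restart reflect the product plus conventional antivirals, and those swabs are the primary data.

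The hole in the Ct bands is a separate and smaller matter. It affects only how a swab is labelled for the primary outcome.

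**Working it through.** The plan gives no calculation on this point, so there is no figure to reproduce. The check sets the passages against example cases.

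**Step 1: how the 4.1 bullets can combine.** A pure OR would make consent alone sufficient, which cannot be meant. Two readings remain: (a) consent plus either the Ct or the adverse-event criterion; (b) all three required.

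**Step 2: example cases.** Ct values are illustrative and consent is taken as given.

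| Case | 3.1 | Section 4 (*only*) | 4.1, reading (a) | 4.1, reading (b) |
|---|---|---|---|---|
| 1. Relapse judged uncontrollable, Ct 28, no related adverse event | restart allowed | barred | not met | not met |
| 2. Related adverse event, Ct 36, no uncontrollable recurrence | not allowed | barred | met | not met |
| 3. Ct 24.9, no related adverse event, relapse not judged uncontrollable | not allowed, unless Ct <25 is itself the recurrence | not barred | met | not met |
| 4. Ct 30 at every swab, no uncontrollable recurrence, no related adverse event | not allowed | barred | not met | not met |

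Case 1 is a conflict between 3.1 and section 4. Case 2 is a conflict between section 4 and 4.1 under reading (a). Case 3 shows that the unstated AND/OR alone changes the answer. In case 4 all sections agree.

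**Step 3: how much primary data one decision can touch.** There are six scheduled swabs per participant. A restart soon after the 1-week swab leaves 6 − 1 = 5 swabs after rescue; a restart soon after the 6-month swab leaves 6 − 5 = 1. With 3 to 6 participants the study plans 3 × 6 = 18 to 6 × 6 = 36 swabs in all.

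**Step 4: the Ct bands.**

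| Ct | Category in the primary outcome | Meets Ct <25 in 4.1? |
|---|---|---|
| above 40 | negative | no |
| 36 to 40 | weakly positive | no |
| 35 to just under 36 | none | no |
| 25 to just under 35 | strong positive | no |
| below 25 | strong positive | yes |

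A value such as 35.5 is not above 40, so it is not negative, but it belongs to neither positive band. The gap has no bearing on rescue, because such a value is clearly not below 25.

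**The case against.** The strongest reply is that section 4.1 can be read as the definition of the recurrence named in 3.1, since 3.1 speaks of a virus recurrence and section 4 of a virus test. On that reading case 1 disappears: a relapse with Ct 28 would not count as uncontrollable. This is possible, but no passage says it. It also leaves case 2 and the AND/OR question untouched, because the adverse-event bullet still does not fit a rule that depends only on the virus test. The conflict in case 1 is conditional on someone judging the relapse uncontrollable, and it should be stated that way.

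A reader might infer several stronger points that the documents do not support:

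- **That the distance between the strong-positive cut-off and the restart value (35 − 25 = 10 cycles) is itself a contradiction.** One cut-off classifies an endpoint and the other triggers treatment. A stricter treatment trigger is a design choice.
- **That a persistently strong-positive eye receives opposite instructions.** Case 4 shows otherwise: without an uncontrollable recurrence or a related adverse event, no section leads to restart.
- **That one decision moves the primary result by 17 to 33 percentage points.** Those figures are one participant out of 6 or out of 3. The plan defines no responder and no primary proportion, so no such result exists to move. A participant restarted at Ct <25 has also already been recorded as strongly positive.
- **That the rule cannot be applied between visits.** The longest nominal interval between swabs is 360 − 180 = 180 days, but nothing forbids an unscheduled swab, and section 4.1 does not require a scheduled one.

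It is also fair to say that section 2.1 selects patients resistant to antivirals, so the effect of restart on later swabs may be modest. The documents give no figure for it.

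**Conclusion.** The point holds as a conflict of wording with consequences for rescue and for the primary data. The restart triggers in 3.1, 4 and 4.1 cannot all be followed: they diverge for a relapse judged uncontrollable with Ct 25 or higher, and for a therapy-related adverse event without a low Ct. The unstated AND/OR widens the ambiguity.

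Its size is best expressed as exposure: between one and five of an affected participant's six scheduled swabs would fall after a rescue decision that depends on the section consulted, in a study planning 18 to 36 swabs. This rests on two assumptions: that such a case occurs in 3 to 6 participants, and that conventional antivirals can change later swab results. The documents quantify neither.

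The band gap is certain, since it follows from the stated cut-offs, but it concerns only the label of values from 35 to just under 36.

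**What to change.** 1. **Reconcile the triggers.** The sponsor should replace the differing texts in 3.1, 4 and 4.1 with one restart statement used in all three places. It should say how the criteria combine (AND or OR), whether an adverse event qualifies without a virus-test result, and whether clinical recurrence without the Ct value qualifies. The investigators decide which passage holds; no threshold or clinical rule is proposed here.
2. **Close the bands.** Make the Ct categories contiguous so that every value has exactly one label. Settle this before results are classified or, if results are already known, say so in the report.
3. **Report the decisions.** In the SAP, add a listing of each restart with its date, reason and most recent Ct, and a list of participants who were strongly positive but not restarted. A reader can then see which swabs came after rescue.
4. **Unscheduled swabs.** Where a tear swab is taken at an unscheduled visit, record it. It should not be a condition for treatment.

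The cost is a wording amendment, which section 10.1 requires the supervising bodies to authorise, and a short listing in the report. No further participants, visits or assays are needed.

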5.1 Quality Control and Quality Assurance

During this study, the Emergency Response Group will conduct regular visits to ensure the protocol and Good Clinical Practices (GCPs) being followed. The monitors may inspect the accuracy of the recorded data through source documents. The investigators and their relevant personnel are available and cooperate during the monitoring visits and possible audits or inspections.

5.2 Monitoring

The potential audits and inspections, including source data verification, must be accepted by representatives designated by the Protocol Chair. Through these audits and inspections, monitors will examine whether the medical activities and documents related to this study were following the protocol, institutional regulation, and any applicable policy requirements. Monitoring will start at the first time of participant registration and will continue during the entire protocol performance.

6. Data Collection and Evaluation

Unless noted, the procedures for all patients must be identical. Any AE/SAE will be documented and reported throughout the study. The period of data collection will be divided into three sections, including pre-study screening, study procedure and post-study follow-up. Screening procedures for baseline data will be taken 3~14 days prior to CRISPR/Cas9 gene editing treatment. An, and institutional Review Board (IRB) approved informed consent document (ICD), must be signed and dated before any specific procedures are done. Results from standard clinical assessments or laboratory tests, prior to the date of informed consent but within the allowed time restraint for screening procedures, can be used for determining the patient's eligibility. The patient's source documents must clearly document the use of pre-consent results. A screening will contain the following items:

- ⑩ Sign form of informed consent
- ⑩ Disease history and prior treatment
- ⑩ Complete ophthalmic examinations
- ⑩ Vital signs
- ⑩ Laboratory evaluation
- ⑩ Other necessary items depending on specific situations

During the study period, each patient will receive corresponding treatment according to the protocol, which was elaborated in the “Study Implementation” section. After the procedure, all the patients will be scheduled a follow-up for 360 days or more, the patients will be followed up 7 ± 2 days, 30 ± 7 days, 60 ± 10 days 90 ± 14 days, 180 ± 21 and 360 ± 31 days after treatment, where their post-treatment status will be carefully evaluated.

7. Statistical Considerations

This is an open-label, single-arm clinical study. The investigators conducted this research to evaluate the safety and efficacy of HSV-1-targeting CRISPR formulation HELP for in vivo treatment of refractory HSK patients. In this study, participants will receive a single dose of HELP formulation by intrastromal injection during the penetrating keratoplasty for acute corneal perforation. At each follow-up point, a series of safety and effectiveness evaluations will be performed.

The primary endpoint, HSV-1 in tear swabs will be evaluated at various test points according to the data collection plan, as summarized by simple descriptive summary. For safety evaluations, clinical examinations (slit-lamp examination, measurement of best-corrected visual acuity, intraocular pressure, B-scan ultrasonography, the time-domain OCT, the spectral-domain OCT, and the ERG) will be presented as simple descriptive statistics in the form of pictures, line charts or summarized tables. Deep sequencing of the corneal epithelial cells (acquired by corneal wipes) will also be reported as descriptively summarized tables. Blood ELISA will be reported graphically with the aid of the Student's test. Other laboratory and imaging correlative studies will also be reported descriptively and graphically.

8. Adverse Event Reporting

8.1 Adverse Event

AE is defined as an undesirable experience or medical condition that occurs after the administration of the procedures or operations specified in the protocol. AE includes all events that may or may not be related to the study. All observed or volunteered AEs regardless of suspected causal relationship to the CRISPR/Cas9 gene editing treatment will be reported as described in the following sections. For all AEs, the investigator must obtain adequate information both to evaluate the outcome of AEs and to assess whether it fits the criteria as a SAE, which requires immediate notification to designated representatives. Follow-ups by the investigator are also required until the event stabilizes at an acceptable level to the investigator.

8.2 Serious Adverse Event Reporting

SAE is an AE with a potential outcome of death, prolonged hospitalization, disability or permanent damage, congenital anomaly/birth defect, or other serious important medical events. Specifically, SAE is any untoward medical occurrence that:

- ⑩ Results in death
- ⑩ Life-threatening
- ⑩ Requires extra hospitalization or prolongation of existing hospitalization
- ⑩ Results in persistent or significant disability/incapacity
- ⑩ Results in congenital anomaly/birth defect

All suspected SAEs related to the study should be followed up according to the institution's standard of care, preferably in consultation with leading specialists.

